6. STUDY DESIGN

This is a randomized, controlled, open-label, parallel group, multi-center, 5-week pilot study to determine changes in BOE in adult smokers allowed *ad libitum* use of VBM-FG2 relative to adult smokers who are not allowed use of VBM-FG2. The data collected from this study will be used to estimate the variability of differences in the percent change from Baseline to the EOS in urinary total NNAL between Test and Control Groups; these findings will be used to estimate the sample size for a future pivotal study. This study will be conducted in approximately 150 adult

smokers who are considered to be in overall good health. Subjects will be randomized (based on gender, daily cigarette consumption [<20 and 20], and quit attempts [any quit attempts/no quit attempts]) to Test (allowed VBM-FG2 use) or Control (not allowed VBM-FG2 use) product in a 3:2 ratio (90 subjects randomized to Test: 60 subjects randomized to Control) with no more than a 60:40 distribution of either males or females to either group.

Screening	Baseline Period*		Product Use Period ^t			
Visit 1	Visit 2	Visit 3	Visit 4	Visit 5	Visit 6	Visit 7
Day -28 to Day -1	Day 1	Day 8±1	Day 15 ± 1	Day 22 ± 1	Day 29± 1	Day 36 ± 1
Subject evaluated against inclusion and exclusion criteria for study eligibility	Baseline CPD data gathered using recall of previous week and daily IVRS call.		Randomization in a 3:2 ratio (Test:Control) 
 • Test = ad libitum VBM-FG2 • Control = no VBM-FG2 			
Enrollment		Randomization				

*Baseline Period = after the daily IVRS call on Day 1 through the daily IVRS call on Day 8.

^t Product Use Period = after the daily IVRS call on Day 8 through the daily IVRS call on Day 36.

Note: Subjects in both groups are allowed to smoke their regular brand cigarettes during the entire study period

Expected duration of the study, from first subject first visit through last subject last visit is approximately 3 months. Expected duration for each subject is expected to be up to approximately 5 weeks (potentially 9 weeks from Screening to EOS). All subjects will be informed that they are allowed to smoke their own cigarettes or to quit smoking during the study.

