11.2 Definition of Baseline for Calculating Change

The Baseline Period is from Day 1 to Day 8. The baseline for calculating change from baseline will be defined in the following table.

Metric	Baseline	Corresponding post-baseline visits
Quit Attempts and Quitting Intentions	Day 1 (Visit 2)	Day 36 (Visit 7)
Fagerstrom Test for Cigarette Dependence (FTCD)	Day 8 (Visit 3)	Day 36 (Visit 7)
BOE	Day 8 (Visit 3)	Visits 4, 5, 6, 7
CPD daily tracking from IVRS	The average of available data from Day 2 through Day 8	Daily CPD Day 9 to 36 or the average of last week at Visits 4, 5, 6, 7
Vital Signs	Day 8, including unscheduled (rechecked) values	Visits 4, 5, 6, 7
*see Section 11.4.3 for more details		

Rationale for the baseline choices for calculating change:

Quit attempts and intentions: Day 1 is the only one measurement in baseline.

FTCD: There are 2 measurements in the baseline, Day 1 and 8. Day 8 is selected because it is anticipated that there will be changes in CPD, a key component of the FTCD score, when adult smokers are asked to track their daily cigarette consumption. Day 1 value does not reflect this change.

BOE: Day 8 is the last of the 2 baseline values and is closer to the post-baseline values.

CPD daily tracking: The weekly average was selected to adjust for the daily variability and also because total NNAL (primary end-point) has a longer half-life and the average CPD might be better representative of changes in exposure to total NNAL than the individual values.

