11.4.1 Statistical Analyses of Primary Endpoint

A linear mixed model for repeated measures analysis of variance will be used for the analysis of the primary outcome measure. SAS procedure Proc Mixed will be used for the statistical computing. The null hypothesis is that smokers allowed *ad libitum* use of VBM-FG2 discs (test) will not differ in the primary biomarker (percent change from baseline to EOS in urinary total

NNAL) compared to smokers not allowed use of VBM-FG2 discs (control). The alternative hypothesis is that smokers allowed *ad libitum* use of VBM-FG2 discs will differ in the primary biomarker compared to smokers not allowed use of VBM-FG2 discs. The model will include percent (or absolute) change from baseline to EOS in urinary total NNAL as a response variable, product, visit, and product by visit interaction as fixed effects; and subject as random effect. In the expanded model, several additional factors will be considered. Details about the models are as follows:

Model 1:

Percent (or absolute) change from baseline in total NNAL = study group + visit + study group*visit + subject + random error

Model 2:

Percent (or absolute) change from baseline in total NNAL = study group + visit + study group*visit + subject + CPD + sex + race + body mass index (BMI) + age + random error

where

CPD = fixed covariate representing average number of cigarettes per day for past week from IVRS

study group = fixed effect term (test or control)

sex = fixed effect (male or female)

race = fixed effect (White or Non-White)

BMI = fixed effect covariate

age = fixed effect covariate (continuous)

visit = fixed effect term representing days (ordinal categorical variable)

subject = random subject effect

baseline = Total NNAL measure at Day 8

If the study group*visit interaction term is not statistically significant (P-value > 0.10), then the interaction term will be removed from the model and all comparisons will be done using the overall product means. If the interaction effect is significant (P-value < 0.10), then the comparisons will be conducted for each study visit. Comparisons between products will be done based on 5% level of significance.

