Least squares mean and standard error for the product effect will be estimated by study group and visit with P-values. P-values will also be provided for other effects in Model 2. While group comparison will be made on multiple visits in the model, the difference in change from baseline to the last visit will be the primary comparison and other comparisons will be secondary.

The models will be applied on both the mITT and the Per-protocol populations.

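### Neither primary NNAL model adjusts for Day 8 NNAL or for all three randomisation factors, a modest and avoidable loss of precision

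*SAP*

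**What the plan says.** The primary endpoint is the Test–Control difference in percent change in total NNAL from baseline to end of study (SAP 11.3.1), with Day 8 as baseline (SAP 11.2). Section 11.4.1 sets out two models:

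- Model 1 is "Percent (or absolute) change from baseline in total NNAL = study group + visit + study group*visit + subject + random error".
- Model 2, described as the expanded model, adds CPD, sex, race, BMI and age.

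The key to the terms contains "baseline = Total NNAL measure at Day 8", but neither equation has a baseline term on its right-hand side. The key also states "CPD = fixed covariate representing average number of cigarettes per day for past week from IVRS", without tying that average to Days 2 to 8 or to the group used at randomisation.

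Section 6 bases randomisation on gender, on daily cigarette consumption in two groups, and on "quit attempts [any quit attempts/no quit attempts". Model 1 has none of the three. Model 2 has sex and the past-week CPD, and quit attempts are in neither model.

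On the contrast, section 11.4.1 says two things. If the group-by-visit P-value exceeds 0.10, "then the interaction term will be removed from the model and all comparisons will be done using the overall product means". It then says that "the difference in change from baseline to the last visit will be the primary comparison and other comparisons will be secondary".

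Section 8 states no power, effect size or SD.

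**The concern.** Each subject's Day 8 value is a single spot-urine measurement, and its error enters that subject's percent change at all of Visits 4 to 7. It therefore does not average out over visits. The random subject effect does not take it out of the group comparison either: with complete data, Model 1's Visit 7 contrast is simply the raw difference in mean percent change. A Day 8 covariate removes part of this error using data already collected. If the randomisation factors predict the response, leaving them out also makes the standard error too large.

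What is at stake is the width of the confidence interval for the primary comparison in a trial of 90 and 60 subjects. A second, separate matter is which contrast is primary, since the two statements in section 11.4.1 can lead to different quantities.

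**Working it through.** **Inputs from the SAP:** 90 Test and 60 Control (section 6; 150 × 3/5 = 90 and 150 × 2/5 = 60), a 5% level and post-baseline Visits 4 to 7. The SAP has no power or variance figure to reproduce.

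**Assumed inputs:** log-normal NNAL; between-subject log SD b = 0.5 or 0.8; spot-sample log SD s = 0.2, 0.3 or 0.4; random-walk drift of SD 0.1 per visit (variance 0.04 by Visit 7); no missing data; a true 20% reduction at all four visits unless stated otherwise.

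**Step 1: gain from the Day 8 term.** On the log scale, the change to Visit 7 has variance 2s² + 0.04 and covariance −s² with Day 8. Adjusting for Day 8 therefore removes s⁴/(b² + s²), and

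gain = (2s² + 0.04) / [2s² + 0.04 − s⁴/(b² + s²)].

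For b = 0.5 and s = 0.4: 0.36 / (0.36 − 0.0256/0.41) = 0.36/0.2976 = 1.21. For b = 0.8 and s = 0.2: 0.12 / (0.12 − 0.0016/0.68) = 1.02.

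The formula is only a guide, because the response is percent change. Model 1 was therefore also simulated on percent change (10,000 trials per scenario). The gain is the variance of the group contrast without the log Day 8 term divided by that with it.

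| b | s | Formula, log scale, Visit 7 | Simulated, Visit 7 | Simulated, overall means |
|---|---|---|---|---|
| 0.5 | 0.2 | 1.05 | 1.04 | 1.07 |
| 0.5 | 0.3 | 1.12 | 1.10 | 1.18 |
| 0.5 | 0.4 | 1.21 | 1.16 | 1.33 |
| 0.8 | 0.2 | 1.02 | 1.02 | 1.03 |
| 0.8 | 0.3 | 1.05 | 1.04 | 1.07 |
| 0.8 | 0.4 | 1.10 | 1.08 | 1.15 |

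Separate simulations under the same assumptions gave 1.02 to 1.17 for Visit 7 and 1.02 to about 1.35 for overall means. The null rejection rate with and without the term differed by at most 0.005.

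**Step 2: power for the last-visit contrast, without and with the Day 8 term.**

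- s = 0.2: 0.97 and 0.98.
- s = 0.3: 0.79–0.80 and 0.81–0.84.
- s = 0.4: 0.55–0.56 and 0.58–0.62.

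The largest gain is 0.62 − 0.55 = 0.07.

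**Step 3: randomisation factors.** If they explain a share R² of the response variance, the gain is 1/(1 − R²). An assumed R² of 2% to 10% gives 1/0.98 = 1.02 to 1/0.90 = 1.11. If randomisation fully balances the factors, the true two-sided error without them is 2[1 − Φ(1.96/√(1 − R²))], which is 0.048 to 0.039. The test is then conservative.

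**Step 4: the two contrasts differ if the effect builds up.** Assume reductions of 5, 10, 15 and 20% at Visits 4 to 7. The expected group difference in percent change at a visit is −(reduction) × exp(s² + drift variance/2), with drift variances 0.01, 0.02, 0.03 and 0.04.

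- s = 0.2: −5.2, −10.5, −15.8 and −21.2; mean −13.2.
- s = 0.4: −5.9, −11.9, −17.9 and −23.9; mean −14.9.

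Overall means thus give about −13 to −15 points, against −21 to −24 at Visit 7. In simulation the interaction was removed in 17%, 44–46% and 64% of such trials at s = 0.2, 0.3 and 0.4.

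**Step 5: the power price of fixing the last visit.** With a constant 20% effect the interaction is removed in 87–88% of trials, and overall means are then the more precise contrast.

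| s | Interaction rule as written, no Day 8 term | Last visit with Day 8 term | Loss |
|---|---|---|---|
| 0.2 | 0.99 | 0.98 | 1 point |
| 0.3 | 0.92 | 0.81–0.84 | 8–11 points |
| 0.4 | 0.74 | 0.58–0.62 | 12–16 points |

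A second simulation gave 0.72–0.73 against 0.59–0.63 at s = 0.4, so the loss is about 1 to 15 points. With the Day 8 term in both analyses, the rule has 0.99, 0.93–0.95 and 0.79–0.84, so the choice of contrast alone costs more (up to 0.84 − 0.62 = 0.22). With the 5/10/15/20% build-up the order reverses: at s = 0.4, 0.48–0.49 for the rule as written against 0.57–0.60 for the last visit with the term.

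**The case against.** The strongest reply is that this is an estimation pilot without a power target, that randomisation keeps the unadjusted comparison valid, and that every magnitude above is assumed. That stands, and it limits the point to an efficiency gain. The low end is also plausible. Section 11.2 says that "total NNAL (primary end-point) has a longer half-life", and section 9 analyses creatinine-adjusted values; both favour stable readings without proving them. In a one-visit calculation with a within-subject correlation of 0.8 or more, the standard error falls by only about 1% to 5%.

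A reader might infer several stronger points that the SAP does not support:

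- **That a baseline term was dropped by mistake.** The key entry for baseline is explained by its role in defining the change score, and section 11.4.2 has a parallel entry.
- **That a third more effective sample size, or 10 power points, is being lost.** Those figures belong to the overall-means contrast or the interaction rule (0.77 to 0.87 and 0.74 to 0.84 at s = 0.4), not to the last-visit difference named as primary.
- **That stratification is known to be exact.** Section 6 says only what randomisation is based on, so the error range in Step 3 is conditional.
- **That covariates plus a fixed last-visit contrast cost only a few degrees of freedom.** Step 5 shows otherwise when the effect is constant.

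**Conclusion.** The point holds as a modest precision loss. Neither primary model uses Day 8 NNAL as a covariate, Model 1 has none of the randomisation factors, and Model 2 lacks quit attempts and uses a CPD value not fixed at baseline. This causes no bias and no Type I inflation.

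For the last-visit contrast the Day 8 term is worth about 2% to 17% in effective sample size and at most about 7 power points; it is negligible at a spot SD of 0.2. Gains of up to about a third apply only if overall means are used. Any gain from the randomisation factors depends on an unknown R². All sizes rest on the assumed log-normal model and variances.

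The disagreement within section 11.4.1 over the primary contrast is a separate estimand question, not part of the precision loss. Holding to the last visit protects the named comparison if the effect builds up, and loses power if it is constant. The SAP gives no basis for knowing which applies.

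**What to change.** Add log Day 8 NNAL and the three randomisation factors, at their values as randomised, to Model 1. Keep percent change as the primary endpoint. This needs SAP wording and model code, uses data collected up to randomisation, and costs a few degrees of freedom.

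Separately, reconcile the two statements on the contrast in section 11.4.1. To keep the named comparison, retain the group-by-visit term and report the last-visit difference as primary whatever the interaction P-value, with overall means as secondary. State the downside: with a constant effect, about 1 to 15 power points relative to the rule as written.

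A supportive log-NNAL analysis for planning the pivotal study is optional. Section 4 allows further analyses later, and this one does not bear on the precision point.

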11.4.2 Statistical Analyses of Secondary Endpoints

Difference in baseline:

Paired T Test will be used to examine the difference in all 5 BOEs between Day 1 and Day 8.

Paired T test will also be used to examine the differences in CPD between the once weekly recall at Day 8 (from questionnaire) and the average daily tracking of CPD from Days 2 through 8 (from IVRS).

Difference in change from baseline:

Linear mixed model for repeated measures analyses of variance will be used for the analyses of the secondary outcome measures: percent change from baseline and absolute change from baseline in all other BOEs. The same model will be used for percent change from baseline and absolute change from baseline in CPD and Total score of FTCD, the model details are as follows:

For other BOEs:

Model 1:

Percent (or absolute) change from baseline = study group + visit+ study group*visit + subject + random error

Model 2:

Percent (or absolute) change from baseline = study group+ visit+ study group*visit + subject + CPD + sex + race + BMI + age + random error

For CPD and Total Score ofFTCD:

Model 1:

Percent (or absolute) change from baseline = study group+ visit+ study group*visit +subject+ random error

Model 2:

Percent (or absolute) change from baseline = study group+ visit+ study group*visit +subject+ sex + race + BMI + age + random error

where

CPD = fixed effect covariate representing average number of cigarettes per day for the past two days from IVRS

study group = fixed effect term (test or control)

sex = fixed effect (male or female)

age = fixed effect covariate (continuous)

race= fixed effect (White or Non-White)

BMI = fixed effect covariate (continuous)

visit= fixed effect term representing days (ordinal categorical variable)

subject = random effect

baseline = Day 8 value for BOE and average of Day 2 to 8 for CPD (IVRS)

If the study group*visit interaction term is not statistically significant (P-value > 0.10), then the interaction term will be removed from the model and all comparisons will be done using the overall product means. If the interaction effect is significant (P-value < 0.10), then the comparisons will be conducted for each study visit.

Least squared mean and standard error for the product effect will be estimated by study group and visit with p-values for statistical significance. P-value will also be provided for other effects in the model.

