All secondary and exploratory analyses will be conducted on the Per-protocol population only.

A linear regression analysis will be conducted within each group at each timepoint to examine the relationships between levels of all 5 BOEs (dependent variable) with either weekly cigarette counts (Day 1 and 8 from questionnaire) or daily cigarette counts (from IVRS) (independent variable). For total NNAL, the corresponding daily cigarette counts from IVRS will be the average of past 7 days. For other biomarkers, it will be the average of past 2 days. The regression analysis will be conducted on the Per-protocol population.

The proportion of subjects in subgroups will be provided with proportion and sample size based on:

- 1) Cigarette consumption change from Baseline (average of Days 2 to 8 from IVRS) to the last week (no change, <50% reduction, 2::50% reduction , 100% reduction, increase);
- 2) Total NNAL change from Day 8 to the last visit (no change, reduction, increase);
- 3) Total scores of FTCD change from Day 8 to the last visit (increase, no change, decrease)
- 4) Proportion of subjects in subgroups based on Changes from Baseline (Day 1) to EOS (increase, no change, decrease) on the change in Quit Attempts from Day 1 to last visit.
- 5) Proportion of subjects in subgroups based on Changes from Baseline (Day 1) to EOS (yes to no, no to yes, and same) on the change in Quitting Intentions from Day 1 to last visit.

The Mantel-Haenszel Chi-Square Test will be used for (1), (2), (3), and (4); Fisher exact test will be used for (5) to test the frequency differences between the two groups.

Additional statistical analyses:

Wilcoxon signed rank test will be used to test the FTCD score difference between the 2 baseline measures (Visit 2 and 3) for the test group. If there is no statistical significance, the average score will be related to the average amount of VBM-FG2 in the past week via linear regression. Otherwise the FTCD score for Visit 3 will be used.

For the test group only, a simple linear regression model will be used to examine the relationship between COHb and Exhaled CO at each post-baseline visit.

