A stepwise multiple linear regression model will also be used to examine the relationship between each of the 5 BOEs (response variable) and a number of factors including average CPD, average VBM-FG2 use, average use of other products, age, sex, BMI and race at each post-baseline visit for the test group only. The average amount of tobacco product use will be for the past 7 days when total NNAL is the dependent variable and will be for the past two days when other BOE is the dependent variable.

Demographics and Characterization of Tobacco Product Use and Exposure Patterns

Demographic baseline characteristics will be summarized by study group with descriptive statistics. For continuous data, descriptive statistics will include N, mean, median, SD, min, max, coefficient of variation (CV%), and 95% confidence interval (CI). For categorical data, frequency counts and percentages will be presented. Fisher's exact test will be used to test for the differences in categorical variables (sex, race: White versus Non-white, quit attempt, cigarette consumption per day: ≤ 20 and > 20) between the 2 study groups and t test, to test for the differences in continuous variables (age, body weight, height, BMI, Number of times stopped smoking cigarettes for 24 hours or longer in an attempt to quit in past 6 months, Number of years smoked since turning 21 years).

Descriptive statistics will be provided to summarize the use of all tobacco products including cigarettes, VBM-FG2 discs and other products by study group and visit. The mean for each variable will be plotted by study group over time.

For subjects in the test group, a simple linear regression model will be used to examine the relationship between visit average of CPD (from IVRS) and visit average of VBM-FG2 use for all post-baseline visits in the study.

For subjects in the test group, a frequency table will be provided with the responses (definitely would buy and probably would buy) in the VBM-FG2 Potential Purchase Interest Questionnaire as the row variable and their average VBM-FG2 use level (4 discs versus < 4) in the last 2 visits as the column variable. Fisher exact test will be used to test for the association.

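### Model 2 adjusts for cigarettes per day with no visit stated; where that means on-study smoking, its group term does not estimate the randomised effect

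*SAP*

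**What the plan says.** Section 11.4.1 gives two mixed models for change in total NNAL. Model 1 contains study group, visit, their interaction and a random subject effect. Model 2 adds CPD, sex, race, BMI and age, with the definition "CPD = fixed covariate representing average number of cigarettes per day for past week from IVRS".

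Section 11.4.2 repeats the pair for the other biomarkers. There the definition is "CPD = fixed effect covariate representing average number of cigarettes per day for the past two days from IVRS". The same list of definitions gives baseline separately, as Day 8 for biomarkers and the Days 2 to 8 average for CPD.

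Section 11.2 defines baseline IVRS CPD as "The average of available data from Day 2 through Day 8" and the matching post-baseline quantity as "Daily CPD Day 9 to 36 or the average of last week at Visits 4, 5, 6, 7".

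On priority, Section 11.4.1 says that "the difference in change from baseline to the last visit will be the primary comparison and other comparisons will be secondary". This fixes the visit but not the model. Both models are run on the mITT and Per-protocol populations. If the interaction has P > 0.10 it is removed, and all comparisons then use overall group means.

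**The concern.** A covariate measured before randomisation leaves the group term as an estimate of the effect of assignment. A covariate measured afterwards, which the product may itself change, does not. CPD is such a variable: Sections 5.3 and 11.3.2 list its change as an outcome to be compared between Test and Control, and Section 11.2 links average CPD to changes in NNAL exposure.

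If Model 2 uses on-study CPD, any part of the product's effect that acts through altered smoking is taken out of the group difference. If CPD and the biomarker also share unmeasured causes, the estimate can move in either direction. The primary objective in Section 5.2 compares groups as randomly assigned, not at equal current smoking. Models 1 and 2 could then report different sizes for the same group difference, with only an implied order to say which one answers the objective.

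**Working it through.** **1. Which days does each window cover?** Days 2 to 8 are 8 - 2 + 1 = 7 days, and the Product Use Period starts after the Day 8 IVRS call (Section 6).

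| Look-back from | Seven-day window (NNAL) | Two-day window (other biomarkers) |
|---|---|---|
| Day 8 (Visit 3) | Days 2-8, the defined CPD baseline | Days 7-8, not a baseline the SAP defines |
| Day 15 (Visit 4) | Days 9-15, on-study | Days 14-15, on-study |
| Day 36 (Visit 7) | Days 30-36, on-study | Days 35-36, on-study |

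**2. Which reading fits the text?** The regressions at each timepoint in Section 11.4.2 use the same pair of windows: "For total NNAL, the corresponding daily cigarette counts from IVRS will be the average of past 7 days" and "For other biomarkers, it will be the average of past 2 days". The stepwise regressions at each post-baseline visit do so again: "The average amount of tobacco product use will be for the past 7 days when total NNAL is the dependent variable", with two days for the other biomarkers. The two-day covariate matches these per-visit windows and differs from the Days 2 to 8 baseline defined in the same list, so on-study is the better reading. For NNAL the same analogy applies, but a look-back from Day 8 gives exactly the defined baseline, so both readings stay open. Section 11.4.2 drops CPD from Model 2 when CPD or FTCD is the response. That fits a baseline covariate as well as an on-study one, so it carries no weight.

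**3. Which model leads?** Section 11.4.1 first describes a single model whose terms are those of Model 1, then introduces Model 2 as an expansion. That implies Model 1, but no sentence says so.

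**4. How far could the two models differ?** The SAP states no effect size, SD or power, so there is no figure to reproduce. From the SAP: 90 Test and 60 Control, Visits 4 to 7, and the 0.10 interaction rule. Everything else here is assumed.

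- Baseline CPD: mean 18, SD 3, 6 or 9, kept within 6 to 45.
- CPD percent change: mean -10 in Control and -10, -20 or -30 in Test; between-subject SD 20, within-subject SD 10; floor -100.
- NNAL percent change = 0.75 x CPD percent change + direct group effect + subject effect (SD 20) + residual (SD 25).
- Total effect = 0.75 x (Test minus Control CPD change) + direct effect: 0.75 x 0 - 15 = -15; 0.75 x (-10) - 7.5 = -15; 0.75 x (-20) + 0 = -15.
- 2000 trials per scenario, random-intercept REML, no missing data; Monte Carlo SE of each mean 0.10 to 0.14.

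Model 1 gave -14.8 to -15.2 in the runs that vary the share acting through CPD. Shrinkage = 1 - (mean Model 2 estimate / mean Model 1 estimate in the same scenario).

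| Share acting through CPD | Model 2, on-study CPD (baseline SD 9 to 3) | Shrinkage (SD 9 / 6 / 3) |
|---|---|---|
| None | as Model 1 | 0% |
| Half | -12.0 to -9.2 | 20% / 26% / 39% |
| All | -8.4 to -2.9 | 43% / 53% / 81% |

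For example, with Model 1 at -15.0: 1 - 9.2/15.0 = 39% and 1 - 2.9/15.0 = 81%.

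Confounding alone (NNAL does not follow CPD; direct effect -15; Test CPD mean -30; baseline SD 6): with a subject-level correlation of -0.5, on-study Model 2 gave -18.1 against -15.0 from Model 1 (18.1/15.0 = 1.21, so 21% larger). With +0.5 it gave -11.9 against -14.8 (1 - 11.9/14.8 = 20% smaller).

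Model 2 with Days 2 to 8 baseline CPD stayed within 0.3% of Model 1.

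**5. A simpler check.** A single-visit regression with different assumed inputs (baseline SD 6, SD of CPD percent change 25, residual SD 30, no direct effect), a 20% CPD reduction in Test and a slope of 0.8, has a true effect of -0.8 x 20 = -16. It returned -16.0 with no CPD term, -16.0 with baseline CPD and -9.5 with on-study CPD: 1 - 9.5/16.0 = 41% removed.

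**The case against.** The strongest reply is that the primary endpoint is where the case is weakest. At Day 8 the seven-day window is the defined baseline, and the covariates beside it (sex, race, BMI, age) are subject characteristics with no visit attached. On that reading Model 2 for NNAL is sound. This stands. A reader might infer that the primary NNAL analysis is adjusted for a post-randomisation variable. The SAP does not support that as a finding: the timing is open, and Model 1, which has no CPD term, is always reported. Nor does the SAP leave priority wholly open, because its order and wording point to Model 1.

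A reader might also infer that Model 2 shrinks the effect by some stated percentage. The simulations do not show that. Their inputs are assumed and their results run from no change to 81% shrinkage, with an increase in one confounding case. They link NNAL to same-visit CPD without lag, although Section 11.2 says NNAL has a longer half-life, so they may overstate what a same-week covariate absorbs. They also hold the group effect constant over visits.

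Adjusting for current smoking can be a legitimate exploratory question. That is a reason to label such a model, and it does not settle what the present covariate means. Even for the two-day covariate, a Days 7-8 reading is conceivable, but the SAP defines no such baseline.

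**Conclusion.** The point holds in limited form. The Model 2 CPD covariate has no stated visit. For the biomarkers other than NNAL it is best read as on-study smoking; for NNAL it may be on-study or baseline. Wherever it is on-study, the Model 2 group term compares groups at equal on-study smoking and does not estimate the effect of assignment. That conclusion needs only that CPD is measured after randomisation and can be affected by the product.

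The direction and size of the gap from Model 1 depend on how much of the effect acts through smoking, on the spread of baseline CPD and on shared causes. The SAP gives none of these, so the simulated figures are illustrative only. Severity is minor to should-fix: the trial is a pilot with no power claim, Model 1 is unaffected and reported in any case, and the harm is a group estimate from Model 2 read as the effect of assignment.

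**What to change.** - **Sections 11.4.1 and 11.4.2, Model 2 definitions:** *CPD = fixed covariate, baseline CPD (IVRS average of Days 2 to 8, Section 11.2).*
- **Section 11.4.1:** *The primary last-visit group comparison is taken from Model 1, with the study group by visit interaction kept for that contrast whatever its P-value; Model 2 is supportive.* The clause on the interaction is needed because the existing rule removes a non-significant interaction, and then no separate last-visit contrast exists.
- **Section 11.4.2:** *Group comparisons are taken from Model 1; Model 2 is supportive.*
- **If the on-study relation is wanted:** keep it as a separate model labelled exploratory, with seven days for NNAL and two days for the other biomarkers, and state that its group term is not read as the effect of assignment.

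The cost is two covariate definitions and one sentence in each of two sections. Baseline IVRS CPD is already collected and defined, and trial conduct does not change. The only downside is one extra labelled model if the on-study relation is kept.
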